#### **SAMPLE SIZE**

Sample size calculations are based on a presumed t-test of refractive cylinder and corneal astigmatism between the two study groups. An alpha of 0.05 and a power of 0.8 were used. The standard deviations of the variables above have been previously estimated at about 0.35D. A difference of 0.25D would be clinically relevant. Using the information above, to reliably detect a difference between groups would require 34 eyes in each group. Spherical equivalent refraction, corneal astigmatism and refractive cylinder are likely to be highly correlated. Allowing for multiplicity of results, approximately 10% more eyes are required per additional correlated endpoint. In this case, 20% more eyes would be required, for a total of 40 eyes (20 subjects) per group.

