#### **STATISTICAL CONSIDERATIONS**

All data will be collected by the research team. Data will be entered into a database. The database will be password protected and access will be restricted to study personnel. Data analysis will be performed without patient identification. Statistical analysis will be done using standard descriptive statistics and other tests as deemed appropriate based on the characteristics of the data to be analyzed. Secondary endpoints will be analyzed only if the primary endpoint demonstrates a statistically significant difference between groups. Corneal and refractive astigmatism are likely to be correlated. A Bonferroni correction will be applied where indicated for evaluating significance. Mean spherical equivalent refraction is not expected to be highly correlated to the measured astigmatism, nor is mean keratometry, so multiplicity considerations will not be required for these variables. All statistical tests will be two-sided and interpreted at a 5% significance level. Comparisons between the two groups will be made. Data analysis will be conducted by a third party consultant.

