**Secondary Endpoints:**

- Residual mean spherical equivalent refraction at 3 months
- Residual corneal astigmatism at 1 month and 3 months
- Residual refractive sphere at 1 month and 3 months
- Interim refractive cylinder at 1 month
- Percentage of eyes with postoperative MRSE accuracy to target  $\leq 0.5D$  at 1 and 3 months
- Uncorrected and best-corrected visual acuity at 1 month and 3 months
- Axis of placement (actual vs. intended)
- Lenstar K's vs. Verion K's
- Corneal incisions stability (manual vs. laser arcs) at 3 months after surgery - based on manifest cylinder and keratometry measurements from 1 and 3 months, noted above.

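### Low correlation is given as the reason to exempt spherical equivalent from multiplicity control; the reason is invalid, the sample-size section contradicts it, and the gate on secondary endpoints should be limited to significance claims

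*Combined protocol and SAP*

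**What the plan says.** The primary endpoint is residual refractive cylinder at 3 months. The secondary list includes "Residual mean spherical equivalent refraction at 3 months" and residual corneal astigmatism at 1 and 3 months.

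Three statements in STATISTICAL CONSIDERATIONS set the multiplicity rules:

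- **Gate:** "Secondary endpoints will be analyzed only if the primary endpoint demonstrates a statistically significant difference between groups".
- **Adjustment:** "Corneal and refractive astigmatism are likely to be correlated", and Bonferroni will be used where indicated. No family or divisor is given.
- **Exemption:** the premise is "Mean spherical equivalent refraction is not expected to be highly correlated to the measured astigmatism". The sentence then brings in a second variable and draws its conclusion for both: "nor is mean keratometry, so multiplicity considerations will not be required for these variables".

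The SAMPLE SIZE section takes the other view of spherical equivalent: "Spherical equivalent refraction, corneal astigmatism and refractive cylinder are likely to be highly correlated". It then states that "approximately 10% more eyes are required per additional correlated endpoint" and concludes "In this case, 20% more eyes would be required, for a total of 40 eyes (20 subjects) per group". The 20% is two steps of 10%, so spherical equivalent is counted as one of the two additional correlated endpoints.

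**The concern.** There are two separate problems.

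1. **The ground for the exemption.** The plan infers from low correlation that no adjustment is needed. The inference runs backwards: highly correlated tests tend to make the same errors together, while weakly correlated tests each add their own chance of a false positive. For spherical equivalent, the premise is also denied by the SAMPLE SIZE section. That conflict does not extend to mean keratometry, which SAMPLE SIZE does not mention and the secondary list does not name.

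2. **The scope of the gate.** Making secondary significance claims depend on a significant primary is sound. The sentence, however, speaks of analysis, not of testing. Taken literally, a non-significant primary would leave the secondaries without even an estimate and interval. OBJECTIVES puts spherical as well as astigmatism outcomes in the main objective, yet every spherical endpoint is secondary. The Lenstar versus Verion keratometry endpoint compares two instruments, not the two groups. Both are read at Visit 1 before randomization and again at Visits 4 and 5, so a treatment-effect gate has no bearing on it.

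At stake are the credibility of any secondary claim on spherical equivalent, and assured reporting of part of the main objective. A third-party consultant will run the analysis and should not have to guess either rule.

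**Working it through.** **Inputs from the documents:** two-sided 5% tests; difference 0.25 D; SD 0.35 D for refractive cylinder and corneal astigmatism; power 0.80; 34 eyes per group, raised to 40. **Assumed, because the documents give no figures:** correlations between test statistics, and a range for primary power.

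**1. The plan's own figures.** A two-sample t-test with effect size 0.25/0.35 = 0.714 needs 31.8, so 32 eyes per group; the stated 34 is within 2. Inflation: 34 × 1.20 = 40.8, against 40 stated. If spherical equivalent is not counted as correlated, the plan's own rule gives 34 × 1.10 = 37.4. The stated 40 exceeds this, so the conflict does not under-size the trial.

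**2. Direction of the correlation argument.** For two null endpoints, each tested at 5% with no gate, the chance of at least one false positive is 1 − 0.95² = 9.75% at correlation 0. From the bivariate normal it is 9.1% at 0.5, 7.8% at 0.8 and 7.0% at 0.9. Error falls as correlation rises. These figures show direction only, because the plan gates every secondary.

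**3. Size behind the gate.** A false secondary claim also needs a significant primary.

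- *Global null:* familywise error stays at 5%, because the primary must be falsely significant first.
- *Spherical equivalent alone, null, independent of the primary:* primary power × 0.05. At power 0.57 this is 2.85% (2.8% to 2.9% by rounding); at 0.88 it is 4.4%. Neither exceeds 5%.
- *Spherical equivalent at 5% plus corneal astigmatism, both null, primary effect real.* With all three independent, the chance is primary power × [1 − 0.95 × (1 − a)], where a is the level for corneal astigmatism. For a = 0.025 the bracket is 0.07375; for a = 0.05 it is 0.0975. When corneal astigmatism is correlated with the primary, the joint probability comes from the bivariate normal, keeping spherical equivalent independent:

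| Primary power | Correlation of corneal astigmatism with primary | Corneal at 2.5% | Corneal at 5% |
|---|---|---|---|
| 0.57 | 0 | 4.2% | 5.6% |
| 0.57 | 0.8 | 4.0% | 5.2% |
| 0.80 | 0 | 5.9% | 7.8% |
| 0.80 | 0.8 | 5.2% | 6.5% |
| 0.88 | 0 | 6.5% | 8.6% |
| 0.88 | 0.8 | 5.7% | 7.1% |

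Power 0.88 is the t-test value for 40 unpaired eyes per group (0.884); 0.80 is the plan's target; 0.57 is an assumed low value. The text does not say which of the last two columns applies.

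**4. Does other text rescue the estimates?** STATISTICAL CONSIDERATIONS promises descriptive statistics and group comparisons in general terms. CONFIDENTIALITY/PUBLICATION OF THE STUDY allows further analysis if the results make it necessary. The first does not exempt secondaries from the gate, and the second permits analysis without pre-specifying any.

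**The case against.** The strongest reply is that the flaw is in the reasoning and hardly touches the results. The gate covers every secondary, spherical equivalent alone is not inflated, and with corneal astigmatism at 2.5% the excess over 5% is at most 1.5 percentage points. The plan itself expects the two astigmatism measures to be correlated; at 0.8 the maximum is 5.7%. If the secondaries were simply labelled supportive, spherical equivalent could still be tested unadjusted, as it is now. This stands, and it is why the point is minor.

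The second reply is that the gate sentence is ordinary gatekeeping language among sentences about significance, and that the documents elsewhere permit further analysis. This also largely stands. The literal reading is possible but probably not what was meant.

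Three stronger readings are tempting and are not supported:

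- *Familywise error near 10%.* That describes two ungated tests, which this plan does not run.
- *An under-sized trial or a compromised primary test.* The stated 40 exceeds the 37.4 implied by the other view, and the primary keeps its full 5%.
- *Secondary results will be suppressed after a negative primary.* The text is unclear about estimates; no sentence clearly forbids reporting them.

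What the replies do not answer is that a stated rule rests on an invalid ground, that the plan contradicts itself on that ground, and that pre-specified secondary estimates are not assured.

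**Conclusion.** The point holds, with minor severity. The correlation-based exemption is unsound for both variables, and for spherical equivalent its premise contradicts SAMPLE SIZE.

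The practical cost is a secondary error of about 4.0% to 6.5% with corneal astigmatism at 2.5%, or about 5.2% to 8.6% with it unadjusted. This assumes a real primary effect, both secondaries null, spherical equivalent independent of the other two, and the stated ranges of power and correlation. The unspecified Bonferroni family makes more difference than the exemption does for spherical equivalent taken alone.

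Confidence is high on the invalid ground and on the contradiction, both of which are plain in the text. It is moderate on the gate, where the sentence is probably shorthand and needs clarifying.

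**What to change.** Before analysis, amend the wording as follows:

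1. Delete the exemption based on correlation, and make SAMPLE SIZE and STATISTICAL CONSIDERATIONS agree on spherical equivalent. Either list mean keratometry as a secondary endpoint or drop it from the multiplicity text.
2. Replace the gate sentence with, for example: *Between-group secondary endpoints are tested for significance only if the primary is significant. Estimates with 95% confidence intervals are reported for every secondary endpoint whatever the primary result. The Lenstar versus Verion keratometry comparison is outside the gate.*
3. Replace Bonferroni where indicated with one of two choices. Either name a short family that includes spherical equivalent (for example with corneal astigmatism, both at 3 months), tested in fixed order or by Holm, with the other secondaries supportive; or label all secondaries supportive without familywise control. The choice is the investigator's.

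**Cost:** no new data and no change in sample size. Always reporting estimates costs no power. Holm's strictest step (2.5%) lowers power for corneal astigmatism from 88% to 82%, taking 0.25 D, SD 0.35 D and 40 unpaired eyes per group, and ignoring the gate. There is no loss if Bonferroni already puts it at 2.5%. The documents give no SD for spherical equivalent, so its loss cannot be computed. A fixed order leaves the first secondary test at the full 5%. Labelling all secondaries supportive costs no power but gives up confirmatory secondary claims.

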#### **Study Endpoints:**

The study endpoints are related to the expected difference between the two groups with regard to the residual refraction after successful cataract surgery.

**Primary Endpoint:**

- Residual refractive cylinder at 3 months

**Secondary Endpoints:**

- Residual mean spherical equivalent refraction at 3 months
- Residual corneal astigmatism at 1 month and 3 months
- Residual refractive sphere at 1 month and 3 months
- Interim refractive cylinder at 1 month
- Percentage of eyes with postoperative MRSE accuracy to target  $\leq 0.5D$  at 1 and 3 months
- Uncorrected and best-corrected visual acuity at 1 month and 3 months
- Axis of placement (actual vs. intended)
- Lenstar K's vs. Verion K's
- Corneal incisions stability (manual vs. laser arcs) at 3 months after surgery - based on manifest cylinder and keratometry measurements from 1 and 3 months, noted above.

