## **OBJECTIVES:**

The main objective of this study is to evaluate spherical and astigmatism outcomes post routine cataract surgery when the complete VERION™ Image Guided System packet + ORA System with VerifEye or VerifEye + are used in the treatment of pre-existing astigmatism using toric intraocular lens (IOL) or corneal incisions compared to the surgeon's standard of care.

Exploratory objective is to evaluate the LRI enhancement feature of the ORA System with VerifEye or VerifEye + in subjects undergoing standard IOL implantation and corneal incisions.

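### The two continuous spherical endpoints are not defined as error from each eye's target, and the only accuracy-to-target endpoint is a dichotomy with less power than the absolute error it is cut from.

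*Combined protocol and SAP*

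**What the plan says.** The Objectives section gives the main aim as to "evaluate spherical and astigmatism outcomes post routine cataract surgery" with the image-guided system and intraoperative aberrometry, against the surgeon's standard of care.

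The primary endpoint is "Residual refractive cylinder at 3 months". Three secondary endpoints concern the spherical result:

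- "Residual mean spherical equivalent refraction at 3 months"
- "Residual refractive sphere at 1 month and 3 months"
- "Percentage of eyes with postoperative MRSE accuracy to target", with a limit of 0.5 D, at 1 and 3 months

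Only the third mentions a target. Under Statistical Considerations, no test or summary measure is fixed for any of them: "Statistical analysis will be done using standard descriptive statistics and other tests as deemed appropriate based on the characteristics of the data to be analyzed". The same section gates them all: "Secondary endpoints will be analyzed only if the primary endpoint demonstrates a statistically significant difference between groups".

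**The concern.** The two arms choose the spherical lens power differently. Under Study Surgery Procedures, Group A uses the surgeon's preferred formula and biometry, and Group B uses the system's planner with an optimized A-constant. A method that plans better should land eyes closer to their intended refraction. Some of that gain may be a smaller average shift, and some may be less scatter on both sides of the target.

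A comparison of signed refractions sees only the first kind. Myopic and hyperopic misses offset each other, so two methods with the same average and different scatter look alike. If an eye's target is not plano, its raw residual refraction also contains the target itself.

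At stake is the interpretation of the spherical part of the objective. A null result on residual MRSE could be reported as equal spherical accuracy when accuracy had not been tested. If signed values were not intended, the choice between signed and absolute error is left until the data are in hand.

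**Working it through.** **The plan's own figure.** The Sample Size section uses a difference of 0.25 D, SD 0.35 D, alpha 0.05 and power 0.80, and states 34 eyes per group. A two-sided two-sample t-test gives 31.76, so 32, which is close. The 20% increase gives 34 × 1.2 = 40.8, against the stated 40. The SD and difference are given for refractive cylinder and corneal astigmatism. None is given for spherical equivalent, so nothing below changes that calculation.

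**Number of pairs.** Each subject contributes one eye to each group. The stated 40 eyes (20 subjects) per group can therefore mean 40 pairs or 20 pairs, and both are shown.

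**Assumptions, not from the documents.** Errors from target are normal with mean zero in both groups. The SD is 0.50 or 0.60 D in Group A and 0.35 D in Group B. The within-subject correlation is 0.3.

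**What each measure sees.** For an error with mean zero and SD σ:

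- Signed mean: 0 in both groups.
- Mean absolute error: σ × √(2/π) = 0.798σ.
- Share within 0.5 D: 2Φ(0.5/σ) − 1.

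| σ (D) | Signed mean | Mean absolute error (D) | Share within 0.5 D |
|---|---|---|---|
| 0.35 | 0 | 0.28 | 84.7% |
| 0.50 | 0 | 0.40 | 68.3% |
| 0.60 | 0 | 0.48 | 59.5% |

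The signed mean is identical across rows. The other two measures both move.

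**Power by simulation**, two-sided 5%: paired t-test on signed error, paired t-test on absolute error, exact McNemar test on within 0.5 D.

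| SD, A vs B (D) | Pairs | Signed | Absolute error | Within 0.5 D |
|---|---|---|---|---|
| 0.50 vs 0.35 | 40 | 5% | 55% | 32–33% |
| 0.60 vs 0.35 | 40 | 5% | 88% | 65% |
| 0.50 vs 0.35 | 20 | 5% | 29% | 12% |
| 0.60 vs 0.35 | 20 | 5% | 55–56% | 28–29% |

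Where two figures are given, repeated runs differed by simulation error.

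**Sensitivity to the correlation**, 0 to 0.5, at 40 pairs. For 0.50 vs 0.35 D, absolute error has 52–62% and the percentage 31–35%. For 0.60 vs 0.35 D, the ranges are 86–93% and 63–70%. The ordering does not change.

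**The case against.** A reader might infer that all the spherical endpoints are group means of signed refraction, and that a real gain in accuracy would go unseen. The documents do not support that, for two reasons.

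- The within-0.5 D endpoint is tied to the target and counts misses in either direction alike. It reaches about 65% power in one of the scenarios above.
- No sentence says that MRSE or sphere will be analysed as signed values or as group means. In mean spherical equivalent, the word mean can belong to the name of a per-eye measure, and the open analysis wording is compatible with absolute error.

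The signed reading is therefore an inference. It is the natural one, because the same list mentions the target only for the percentage, and because the Sample Size section counts spherical equivalent among the endpoints of a calculation built on a t-test.

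Four further points have weight:

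- The objective does not itself define the spherical outcome as accuracy to target. That link comes from what the two arms do differently.
- The 5% for the signed test follows from setting both means to zero. It is simply the test's alpha. A systematic shift is plausible here, since only Group B is described as using an optimized A-constant, and a signed comparison would address it.
- Nothing says that targets differ by group. With the first eye randomized and the fellow eye given the other method, differing targets would mainly add noise, not bias.
- These endpoints are secondary and are analysed only after a significant cylinder result.

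These points limit the consequence. They do not remove the gap: no continuous measure of accuracy to target is defined.

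**Conclusion.** The point holds in a limited form. Residual MRSE and residual sphere are not expressed as error from target. If analysed as signed refractions, they cannot detect reduced spread. The listed percentage endpoint can, at a cost in power against absolute error of roughly 22 percentage points (SD 0.50 vs 0.35 D) or 23 (0.60 vs 0.35 D) at 40 pairs. At 20 pairs the cost is about 17 and 27 points, and the percentage would probably miss even the larger gain.

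These sizes rest on assumed SDs, zero mean error, normality and a correlation of 0.3. The direction of the result held in every scenario run. The primary cylinder analysis and the stated sample size are not touched. This is a worthwhile clarification of the secondary endpoints, not a flaw in the trial's main comparison.

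**What to change.** In Secondary Endpoints, define the continuous spherical endpoint as absolute error at 3 months: |achieved MRSE − the target refraction planned for that eye|. State that it is compared within subject, for example by a paired test on the difference between the two eyes.

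Keep the signed error from target as a check for systematic shift, and the percentage within 0.5 D as supportive. For residual sphere, say whether it is raw refraction or error from target, and whether it is signed. Record each eye's target before randomization, when the plan has all calculations completed.

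The cost is wording. Manifest refraction is already taken at Visits 4 and 5, and the percentage endpoint already needs each eye's target. No visit, measurement or subject is added.

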## 5. Study Surgery Procedures

Eyes of the study participants will be randomly assigned to one of two groups:

- a. Group A, surgeon standard of care prior to getting VERION™ Image Guided System. Spherical power will be selected using the surgeon's preferred formula (Haigis, Holladay 2, Holladay, or other) and biometry method (IOL Master, Lenstar). Astigmatism correction will be planned using the surgeon's preferred keratometry method and calculator/nomogram to determine toric power and corneal incisions (i.e. Alcon toric calculator, Holladay toric calculator, AMO LRI calculator, etc). At time of surgery, axis of placement will be marked using blue ink marks. Corneal incisions will be made manually.
- b. Group B, VERION™ Image Guided System: Digital Surgical Planning and Positioning Tools + ORA System with VerifEye or VerifEye +. Spherical power of the IOL will be selected using the Verion™ Planner with the surgeon's preferred formula with an optimized A-constant (Haigis, Holladay 2, Holladay, or other). Both toric lenses and corneal incisions will be calculated with the Verion™ Planner using the Verion™ Reference Unit keratometry and white to white measurements, and Lenstar biometry. The VERION™ Digital Markers L and M will be used for axis of placement and confirmed using ORA System with VerifEye or VerifEye +.

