4. Visit 4 and 5: Assessment will include uncorrected and best-corrected ETDRS visual acuity (UCVA / BCVA), manifest refraction, auto refractor keratometry, Lenstar, VERION™ Reference Unit, corneal topography, intraocular pressure, and slit lamp examination. The location of all corneal incisions as well as toric IOL orientation will be documented.

Adverse events and device deficiencies/quality complaints will be monitored and recorded at all study visits.

**Table 1.** Visits and Study Assessments

Study Assessments	Visit 1 Preoperative	Visit 2 Operative	Visit 3 Day 1	Visit 4 Day 20-40	Visit 5 Day 75-105
Inclusion/Exclusion Criteria	x				
Consent Subject	x				
Patient demographics (age, gender, race, ethnicity)	x				
Manifest Refraction	x			x	x
UCDVA	x		x	x	x
BCDVA	x			x	x
Tonometry (IOP)	x		x	x	x
Complete slit lamp exam	x		x	x	x
Dilated fundus exam	x			†	†
Auto refractor keratometry	x			x	x
Atlas corneal topography	x			x	x
Lenstar LS900 measurements	x			x	x
Verion™ Reference Unit measurements	x			x	x
Verion™ Planner	x				
Alcon Toric calculator	x				
LRI calculator	x				
Incision Size and Location		x			
Record Lens Model Implanted (Attach label, or record manufacturer, model, power)		x			

VerifEye or VerifEye + information		x			
Post-IOL implantation incision size		x			
LenSx parameters		x			
Corneal arcs/toric IOL orientation		x	x	x	x
Adverse events / device deficiency	x	x	x	x	x

x To be performed as scheduled

† To be performed as deemed necessary by the investigator.

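### Residual corneal astigmatism has no named instrument, and in corneal-incision eyes a reading on either group's planning keratometer favors that group

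*Combined protocol and SAP*

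**What the plan says.** The Secondary Endpoints list contains "Residual corneal astigmatism at 1 month and 3 months" with no device and no derivation. Section 6.b gives the Visit 4 and 5 assessments as "manifest refraction, auto refractor keratometry, Lenstar, VERION™ Reference Unit, corneal topography, intraocular pressure, and slit lamp examination", and Table 1 confirms that all four corneal devices are used at both visits. Nothing states which device supplies the endpoint, whether readings are averaged, or whether every eye is read on the same device. Statistical Considerations leaves the choice of tests open and does not address the instrument.

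The planning devices differ by group (Section 5). Group B toric lenses and incisions are "calculated with the Verion™ Planner using the Verion™ Reference Unit keratometry". For Group A, "Astigmatism correction will be planned using the surgeon's preferred keratometry method", and that method is not fixed.

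Two other secondary endpoints bear on this. One is "Lenstar K's vs. Verion K's", so the plan itself allows that devices may disagree. The other is corneal incision stability, "based on manifest cylinder and keratometry measurements from 1 and 3 months, noted above", which has the same gap.

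**The concern.** An open choice of keratometer would usually be a missing detail. Here it is directional, because one candidate is part of the test article and planned one group's eyes. If a device misreads an eye in a repeatable way, an incision plan built on it leaves that error on the cornea with the opposite sign. The same device then fails to see it, while the fellow eye, planned on another device, shows the errors of both. Two equally accurate planning methods would look different, and the reading device would decide which looks better.

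Corneal astigmatism is named beside refractive cylinder as a basis of the sample size. After a significant primary result it would be the natural corroboration. A Group B advantage read on VERION would then be partly circular, and a reading on Group A's planning device could mask a real one.

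**Working it through.** **The plan's own figures.** The plan gives no figure for device error. Its yardstick is the Sample Size section: difference 0.25 D, SD 0.35 D, alpha 0.05, power 0.8, 34 eyes per group. A two-sided two-sample t-test gives 31.76, so 32, close to 34; and 34 × 1.2 = 40.8 against the stated 40. The point does not depend on these; only the 0.25 D is used below.

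**Model for incision eyes.** Work per vector component. Let v and a be the persistent errors of the VERION unit and of Group A's planning device for an eye, and r all other residual error, with the same distribution in both groups. The cornea is left with r − v in Group B and r − a in Group A. With equal error sizes there is no true group difference.

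- Read on VERION (add v): Group B shows r; Group A shows r − a + v.
- Read on Group A's device (add a): Group A shows r; Group B shows r − v + a, the mirror image.
- Read on a third device with independent error t: r − v + t against r − a + t, so the expected difference is zero.

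**Inputs, all assumed:** SD of r = 0.30 D per component; v and a independent, each with SD e = 0.1, 0.2 or 0.3 D; no screening for device disagreement. The mean magnitude of a centered bivariate normal is SD × √(π/2) = SD × 1.2533.

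Group B read on VERION: 0.30 × 1.2533 = 0.376 D. Group A has SD √(0.09 + 2e²):

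| e (D) | Group A SD | Group A mean (D) | Spurious A − B (D) |
|---|---|---|---|
| 0.1 | √0.11 | 0.416 | 0.04 |
| 0.2 | √0.17 | 0.517 | 0.14 |
| 0.3 | √0.27 | 0.651 | 0.28 |

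**Second model.** A simulation of 400,000 eyes per cell gave each planning device a fixed bias b of equal size in a different direction, with random measurement error 0.15 D and surgical error 0.20 D per component (assumed). Read on VERION, Group B averaged 0.365 D and Group A 0.387, 0.446 and 0.537 D at b = 0.1, 0.2 and 0.3. The differences are 0.02, 0.08 and 0.17 D. They reversed sign on Group A's device and were about zero on a device that planned neither group. Toric eyes showed about zero at every b, because a toric lens does not correct the cornea and planning error does not reach corneal astigmatism.

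**What shrinks the effect.**

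- *Toric share.* The documents give none. At an assumed one half, the first model's figures halve to 0.02, 0.07 and 0.14 D.
- *Screening.* Section 6.b excludes subjects whose preoperative measurements disagree, with no threshold. If eyes whose two planning devices differ by more than an assumed 0.5 D were dropped, simulation of the first model gives about 0.04, 0.09 and 0.10 D. The share kept is 1 − exp(−0.5²/4e²): 79% at e = 0.2 and 50% at e = 0.3. A screen that tames the largest case would therefore discard half the eyes.

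**Limit of a third device.** If its error correlates 0.5 with Group A's planning device, Group A's SD becomes √(0.09 + e²) and Group B's stays √(0.09 + 2e²). The means are 0.396 against 0.416, 0.452 against 0.517 and 0.532 against 0.651 D, so Group A is favored by 0.02, 0.06 or 0.12 D. This is smaller than the bias from reading on a planning device, but not zero.

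**The case against.** The strongest reply is that little rests on this endpoint. The primary endpoint is refractive cylinder at three months, which needs no keratometer, and secondary endpoints are analyzed only after a significant primary. The consistency review before randomization screens on the disagreement that drives the bias. ORA is used in Group B to confirm axis placement, and its incision-enhancement feature is an exploratory objective; any change it makes to the incision plan breaks the exact cancellation assumed above. Only incision eyes are exposed, and only the most extreme assumed input passes 0.25 D.

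All of this stands, and it limits the weight of the point. It does not remove it. The gate opens exactly when a corroborating corneal result would be quoted, the review has no threshold, and the documents do not say how often ORA would alter the plan.

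A reader might infer that the trial's main comparison is tilted toward VERION, or that VERION readings will be used. The documents support neither: the primary is untouched, no instrument is chosen, and the bias can run either way. A reader might also infer that the outcome device should be barred from Group A planning. That would change the comparator, which Section 5 defines as the surgeon's own standard, and it is not needed.

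**Conclusion.** The point holds for a gated secondary endpoint, and for the keratometry part of incision stability. The instrument is unspecified, and in corneal-incision eyes a reading on a planning device is biased toward the group planned on it. The direction follows from the design whenever devices have persistent, device-specific error; independent random error is not hidden in this way. The size rests on assumptions outside the documents: about 0.04 to 0.28 D in incision eyes without screening under one error model, and 0.02 to 0.17 D under another, for device errors of 0.1 to 0.3 D. The 0.28 D figure is the top of an assumed range and should not be read as the expected bias. In the trial as run it would be smaller, by an amount the documents do not allow one to compute. Toric eyes and the primary endpoint are not affected. The change is worth making because it costs almost nothing.

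**What to change.** Before the first surgery, add to the Secondary Endpoints one sentence naming a single non-VERION instrument from Table 1 for residual corneal astigmatism, chosen because it is not expected to be Group A's planning keratometer. Atlas topography is an example; if the surgeon plans Group A on topography, the autokeratometer would serve. Use it for all eyes at both visits and for the keratometry part of incision stability. Record the Group A planning device for each subject, so that independence can be checked. Report VERION, Lenstar and the remaining readings as sensitivity analyses only. Leave the surgeon's choice of Group A planning device unrestricted.

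The cost is that sentence, one recorded item and a few extra tables, since all four measurements are already scheduled. The remaining weakness is that the chosen instrument may not be fully independent of Group A's planning device; the recorded device and the sensitivity analyses would help to show whether that matters.
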